1.2 Known risk factors for locoregional recurrence

1.2.1 The extent of surgery does not influence locoregional recurrence rate

Multiple studies have examined potential factors which influence the risk of patients developing LRR. As would be expected, patients who at primary diagnosis present with a larger primary tumour and nodal metastatic involvement[12] are at higher risk of LRR. The aim of breast cancer surgery is to resect the tumour with clear margins (i.e. with no tumour at the cut surface). Depending upon the primary tumour size to breast volume ratio, patients are offered breast conserving surgery (BCS) or mastectomy with or without breast reconstruction. This is based on historic randomised control trial data (patients recruited from 1973 and 1980), which showed no difference in long term survival (breast cancer specific and overall survival) for patients who were treated with BCS and whole breast radiotherapy (WBRT) versus mastectomy[13]. 20 year follow up of these patients demonstrated higher crude cumulative local recurrence incidence for patients who received BCS and WBRT versus mastectomy (8.8% versus 2.3%). However, with improved modern therapy, the rate of LRR after BCS and WRBT has fallen considerably with contemporary reported 5 year LRR rates ranging from 2 to 4%[3, 14, 15]. This rate remained stable at 5% at 10 years as reported Bosma et al, who followed up 8485 patients treated with BCS and WBRT at the Netherlands Cancer Institute[14]. Furthermore, analysis of the National Surgical Adjuvant Breast and Bowel Project (NSABP) randomised clinical trials showed that for patients with large cancers (>5cm), the 10 year cumulative incidence of LRR was 7.1% for patients who were treated with mastectomy[16]. Therefore, the extent of surgery does not significantly influence LRR rate with no differences observed in long term patient survival.

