For patients who undergo BCS and WBRT, achieving clear margin reduces local recurrence rate. However, achieving a wider margin width does not influence local recurrence rate. Houssami et al carried out a meta-analysis of over 28,000 patients and demonstrated that margin widths of 1, 2, or 5mm did not affect local recurrence rates [17]. However, the relative risk of developing a local recurrence was 2.44 for involved versus clear margins. Similarly, a Danish cohort study of 11,900 patients determined that having an involved margin was associated with more than twofold risk of local recurrence for patients who had undergone BCS for invasive cancer[18].

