- 2.8 If sentinel lymph node biopsy, method of localisation (dual technique with blue dye and radioisotope / radioisotope alone / blue dye alone / other methods)
- 2.9 Was the original breast cancer inflammatory breast cancer (Yes/No)

Pathology

- 2.10 Tumour subtype (invasive ductal / invasive lobular / mixed ductal and lobular / other subtypes / pure ductal carcinoma in situ)
- 2.11 Tumour grade (1 to 3 for invasive / low to high grade for ductal carcinoma in situ)
- 2.12 Tumour size (in mm; invasive tumour size, unless DCIS)
- 2.13 Multifocal or multicentric cancer (Yes/No)
- 2.14 Lymphovascular invasion (Yes/No)
- 2.15 Closest radial margin after final surgery (in mm)
- 2.16 Were anterior or posterior margins close (1mm or less)? If Yes, please state which (anterior / posterior / both) and distance in mm (0,1)
- 2.17 Number of positive axillary nodes (state macro- or micrometastasis)
- 2.18 Number of axillary lymph nodes retrieved
- 2.19 Oestrogen receptor Allred score (ER; 0 to 8; please state if any other scoring system was used and its score; e.g. H-score)
- 2.20 Progesterone receptor Allred score (PR; 0 to 8; please state if any other scoring system was used and its score; e.g. H-score)
- 2.21 HER2 receptor status (Positive or negative; please state immunohistochemistry score 0/1+/2+/3+; if 2+ was FISH test done? What was the final HER2 receptor status if FISH test done; positive/negative/not applicable)
- 2.22 Ki67 test? If Yes, please state %

Adjuvant treatment

- 2.23 Receipt of radiotherapy after breast conserving surgery or mastectomy (Yes/No/Not applicable)
- 2.24 If radiotherapy after breast conserving surgery, please state radiotherapy regimen (whole breast radiotherapy; 40 Gy in 15 fractions / whole breast radiotherapy; 27Gy in 5 fractions (hypofractionated) / partial breast radiotherapy / whole breast radiotherapy with boost)
- 2.25 Radiotherapy to the axilla (Yes/No)
- 2.26 Supraclavicular fossa radiotherapy (Yes/No)
- 2.27 Internal mammary node radiotherapy (Yes/No)
- 2.28 Receipt of adjuvant endocrine therapy (Yes/No)
- 2.29 If receiving or received endocrine therapy, please state duration received (total number of years)
- 2.30 Please state first line endocrine therapy (tamoxifen / letrozole / anastrozole / exemestane / ovarian suppression / others; please specify)
- 2.31 What was the duration of the first line endocrine therapy? Please state number of years

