- 3.29 If repeat sentinel lymph node biopsy was performed, was it successful in identifying the sentinel lymph node (i.e. was a 'hot' and/or blue lymph node identified?; Yes/No)

3.30 If unsuccessful and no sentinel lymph node was identified during surgery, how did you proceed (no further axillary dissection / axillary node sampling / axillary node clearance)

LRR pathology

- 3.31 Multifocal or multicentric cancer (Yes/No)
- 3.32 Lymphovascular invasion (Yes/No)
- 3.33 Tumour size (invasive size in mm, unless DCIS)
- 3.34 Closest radial margin (in mm)
- 3.35 Were anterior or posterior margins close (1mm or less)? If Yes, please state which (anterior / posterior / both) and distance in mm (0,1)
- 3.36 Number of positive axillary nodes (state macro- or micrometastasis)
- 3.37 Number of lymph nodes retrieved

Adjuvant treatment for LRR (including further surgery)

- 3.38 Was further surgery to the breast required (Yes/No). If Yes, please state the type of further breast surgery (re-excision of margins / mastectomy)
- 3.39 Was further surgery to the axilla required (Yes/No). If Yes, please state the type of further axillary surgery and date (axillary node clearance / sentinel lymph node biopsy/ axillary node sampling)
- 3.40 Receipt of breast radiotherapy (Yes / No/ not applicable)
- 3.41 If radiotherapy after breast conserving surgery, please state radiotherapy regimen (whole breast radiotherapy; 40 Gy in 15 fractions / whole breast radiotherapy; 27Gy in 5 fractions (hypofractionated) / partial breast radiotherapy / whole breast radiotherapy with boost)
- 3.42 Post-mastectomy radiotherapy (Yes/No/ not applicable)
- 3.43 Radiotherapy to the axilla (Yes/No)
- 3.44 Supraclavicular fossa radiotherapy (Yes/No)
- 3.45 Internal mammary node radiotherapy (Yes/No)
- 3.46 Receipt of endocrine therapy (Yes/No)
- 3.47 If receiving endocrine therapy, please state the duration recommended at the MDT meeting (number of years)
- 3.48 What endocrine therapy was the patient prescribed (tamoxifen / letrozole / anastrozole / exemestane/ ovarian suppression / others; please specify)

- 3.49 Receipt of chemotherapy (Yes/No)
- 3.50 Please select which chemotherapy agents the patient received (epirubicin / doxorubicin / docetaxel / paclitaxel / cyclophosphamide / carboplatin / capecitabine / others; please state)
- 3.51 Receipt of anti-HER2 treatment (Yes/No). If Yes, was it trastuzumab (Herceptin) or trastuzumab (Herceptin) and pertuzumab (Perjeta)?

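### The anterior/posterior margin items (2.16 and 3.35) list only 0 and 1 mm, so a margin between the two has no code and may be recorded as involved or as clear, depending on the site

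*Protocol*

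**What the plan says.** Section 5 (Data collection) carries the same item twice: 2.16 for the original cancer and 3.35 for the locoregional recurrence (LRR). Each first asks "Were anterior or posterior margins close (1mm or less"). On a Yes, the site is told to "please state which (anterior / posterior / both) and distance in mm (0,1").

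Section 1.2.1 supplies the definition. The aim of surgery is to achieve "clear margins (i.e. with no tumour at the cut surface"). The same section reports from a meta-analysis that "margin widths of 1, 2, or 5mm did not affect local recurrence rates", whereas "the relative risk of developing a local recurrence was 2.44 for involved versus clear margins".

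The neighbouring radial margin items (2.15 and 3.34) ask for a distance in mm with no listed values. Section 6 requires every field to be completed and every entry to be verifiable in the source documents.

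**The concern.** The first part of each item admits every distance from 0 to 1 mm. The second part offers only the two ends of that interval. A margin strictly between them has to be forced into one end, and one of those ends is the value that means tumour at the cut surface.

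Involved versus clear is the margin contrast to which Section 1.2.1 attaches risk. The margin data serve the objective on risk factors related to the primary cancer and its management (Section 2.3, objective 2(ii), and Section 4.3) and the evaluation of prognostic factors (objective 2(iii)). If some sites round down and others round up, a 0 in the anterior/posterior field does not mean the same thing across the 50 or more units. An analysis plan cannot repair this later, because the distinction would not be in the dataset.

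**Working it through.** There is no plan figure to reproduce and no arithmetic to run. The check is a comparison of texts in three steps.

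**1. Is (0,1) a list or an interval?** Elsewhere Section 5 writes ranges with the word to: Allred scores 0 to 8, performance status 0 to 4, invasive grade 1 to 3, biopsy categories 1 to 5. It separates options with slashes or commas; menopausal status (item 1.3) and recurrence location (item 3.11) use commas. By that usage (0,1) is a list of two permitted values.

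**2. Does every admissible distance have a code?**

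| Distance on the pathology report | Status under Section 1.2.1 | First part of item | Matching code | What the dataset may hold |
|---|---|---|---|---|
| 0 mm | involved | Yes | 0 | 0 |
| above 0, under 1 mm (e.g. 0.3 mm) | clear | Yes | none | 0 or 1 |
| 1 mm | clear | Yes | 1 | 1 |
| above 1 mm | clear | No | not needed | No |

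The second row is the gap. Section 6 does not allow the field to be left empty, and no rounding rule is given.

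**3. What follows from each way of filling the gap?**

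- The site rounds down: 0 holds both involved and clear margins, and the contrast is blurred.
- The site rounds up: 0 holds involved margins only. The contrast is intact, and only the distance is coarse.
- The site rounds to the nearest whole mm: some clear margins go to 0 and the rest to 1.
- Sites differ: the meaning of 0 varies by unit.

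No other item in Section 5 records anterior or posterior involvement, so the dataset cannot undo the first or third case. The unit-exclusion rule in Section 6 rests on agreement in the number of cases, so it would not detect this. Someone validating the sampled records would also have no stated rule by which a 0.3 mm margin entered as 0, or as 1, is wrong.

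A side point: when both margins are close, the prompt as written mentions one distance for two margins. Whether the form provides two fields cannot be seen.

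**The case against.** Several counter-arguments carry weight.

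- The REDCap form is not shown. It may accept decimals, and (0,1) may be shorthand for an interval. This stands as a caveat. The protocol's notation points the other way, and even on the interval reading the wording is ambiguous enough to need clarifying.
- The items never label 0 as involved. That is true; the link comes from the definition in the background section. But 0 is the only value on offer that can stand for tumour at the cut surface.
- Sites that keep 0 for tumour at the cut surface and enter 1 for every close but clear margin preserve the contrast exactly. This stands, and it is why only possible misclassification can be claimed.
- The pathology report remains available as source. This also stands. It makes a look-back possible but does not correct the analysis dataset.

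A reader might infer more than the text supports, in two ways. The first is that the relative risk of 2.44 will be diluted by some calculable amount. It will not: that figure is the risk of developing a local recurrence after breast conserving surgery with whole breast radiotherapy. Every MARECA participant already has a recurrence, and Section 8 itself says there is no denominator for a recurrence rate, so the study does not estimate that quantity. Nor is 2.44 a prognostic effect after LRR surgery. The cited finding of no width effect covers 1, 2 and 5 mm and says nothing about margins under 1 mm. The second is that the share of involved original margins is definitely overstated. That would be so only where sites round down, and the documents do not say what sites do.

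**Conclusion.** The point holds as a defect in the stated response set of two data items. A margin above 0 and under 1 mm has no valid code, so involved and clear anterior/posterior margins may be confused, and differently by site.

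The size cannot be given. It would need the share of anterior/posterior margins falling between 0 and 1 mm and the share of sites that enter these as 0, and the documents give neither.

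The reach is small. The primary endpoint and the sample size do not depend on these items. Margin status is not among the covariates that Section 8 names for the comparison by type of initial surgery. Radial margins are recorded freely in mm for both cancers. What is exposed is the secondary work on risk factors and prognostic factors, for anterior and posterior margins only.

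The conclusion rests on two assumptions: that (0,1) is a two-value list, as the protocol's notation suggests, and that the data-entry form follows the protocol wording. It is a cheap improvement, not a threat to the study's main question.

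**What to change.** In items 2.16 and 3.35, replace (0,1) with a status recorded separately for the anterior and the posterior margin, in one of two ways:

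- three categories: involved (tumour at the cut surface), clear by less than 1 mm, clear by 1 mm; or
- a distance in mm that accepts decimals, with a separate tick for involved.

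The categories need less of the site, because they can be completed when the report says only that the margin is under 1 mm.

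Check any anterior/posterior entries already coded 0 or 1 against the pathology report. Those coded 0 come first, since that is where involved and clear may be mixed; those coded 1 matter for separating under 1 mm from 1 mm.

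The cost is a form change for two items and a limited look-back at sites.

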7.1 Source data

Source documents are where data is first recorded, and from which participants' data are obtained. These will include, but are not limited to, hospital records (from which medical history and previous and concurrent medication may be summarised into the REDCap database or the CRF), clinical and office charts, laboratory and pharmacy records, diaries, microfiches, radiographs, and correspondence. Source data verification will be monitored to confirm compliance with the protocol and the protection of patients' rights as detailed in the Declaration of Helsinki 1964 as amended October 1996. Monitoring by the Chief Investigator or authorised authorities will be to ensure

- Sufficient data is recorded to enable accurate linkage between hospital records and CRFs/REDCap database
- Source data and all trial related documentation are accurate, complete, maintained and accessible for monitoring and audit

• Staff working on the trial will meet requirements of the EU Directive

7.2 Access to data

Direct access will be granted to authorised representatives from the Sponsor, host institution and the regulatory authorities to permit trial-related monitoring, audits and inspections.

7.3 Data recording and record keeping

All information collected during the course of the study will be kept strictly confidential. The information governance team (including the trust's Caldicott guardian) at Leeds Teaching Hospitals NHS Trust has reviewed the study protocol, and we have obtained Caldicott approval for the study.

Information will be held securely on paper and electronically at each participating NHS Trusts. All participating sites will comply with all aspects of the Data Protection Act 2018 and operationally this will include:

- consent from patients to record personal details including name, date of birth, address and telephone number, email address, NHS ID and hospital ID
- appropriate storage, restricted access and disposal arrangements for patient personal and clinical details
- consent from patients for access to their medical records by responsible individuals from the research staff, the sponsor, and from regulatory authorities, where it is relevant to trial participation
- Consent from patients for the data collected for the trial to be used to evaluate safety and develop new research.

Data completeness is an integral part of any study. A CONSORT style will be used to monitor data completeness from eligibility screening, approach, study acceptance through to the final follow-up visit. This information will be made available to the study steering group as regular reports. The team will also report the number of:

- Patients screened per month
- Patients approached per month (and reasons why not approached)
- Patients recruited per month
- The number of patients who complete each follow up visit or are lost to follow-up
- The number of patients who complete the trial.

8. Sample size and data analysis

All data analysis will occur centrally and will be led by the steering group. Local collaboratives and hospital trusts will have ownership of their own data and will be able to present it locally if they so wish. Summary statistics will be calculated for each participating Trust and fed back to individual units to allow comparison with national averages and ranges. It is important to note that we cannot determine locoregional recurrence rate for each unit or at national level. We will not have a denominator to determine this rate.

Descriptive summary statistics will be calculated for each outcome and regression analysis used to control for predictive variables. Data will be tested for distribution and differences between groups using unpaired t-tests, Mann-Whitney U tests and Chi squared tests as appropriate. Based on the NCRAS report described in section 1, approximately 250 patients were diagnosed with LRR with or without distant metastasis across 15 UK breast units over 6 months. This data suggests that around 33 patients will be eligible for recruitment over 12 months in each breast unit. This potential sample size has been corroborated from data at Leeds Teaching Hospitals NHS trust (LTHT) where 28 patients met the eligibility criteria (January 2019 to December 2019). This was based on information from the LTHT cancer information team. There are 144 breast units in the UK and at least 50 units so far have agreed to participate in the study. Given the variable number of cancer patients treated per year in these participating units, we would anticipate each unit to recruit 5 to 10 patients over 12 months. Therefore, we would aim to recruit at least 500 patients diagnosed with LRR +/distant metastasis over 24 months. There are no statistical criteria for stopping the study early as the study is observational in nature examining current UK practice and therefore low risk.

One of the key aim of the study is to determine whether patient prognosis after their LRR diagnosis (without distant metastasis) differs according to the type of breast cancer surgery (mastectomy versus BCS and radiotherapy) for the initial cancer. Based on published studies[36, 37, 39], the distribution of patients presenting with LRR is almost even between mastectomy and BCS for the initial cancer (40% mastectomy and 60% BCS). From these published studies, the 5 year DFS after treatment for LRR has been reported to be approximately 70%[67, 68]. A single centre retrospective study by Shenouda *et al*[39] identified that patients initially treated with BCS and radiotherapy had improved DFS by

approximately 20% as compared to patients initially treated with mastectomy and no radiotherapy (5 year DFS of 80% vs. 60%).

Power calculation was performed to determine sample size in each group (patients treated with mastectomy versus BCS and radiotherapy for the initial cancer), using logistic regression analysis to adjust for other covariates stated in the background section (tumour and nodal staging, molecular receptor profile, and tumour grade). This calculation has determined that the estimated sample size for each group would be 165 patients. Therefore, a subset of 330 patients diagnosed with LRR without distant metastasis will require recruiting to the study to determine whether patient prognosis differs according to the type of breast cancer surgery performed for the initial cancer. This falls well within the minimum patient recruitment target of 500 patients who are diagnosed with LRR +/- distant metastasis.

Kaplan Meier survival analysis will be performed at the two study time points (3 and 5 years after diagnosis of LRR). We will determine DFS/PFS/OS for the study participants. DFS will be determined for patients diagnosed with LRR without associated distant metastasis at presentation who then subsequently undergo LRR resection. PFS will be determined for patients diagnosed with LRR with associated distant metastasis at presentation. OS will be determined for the whole study cohort (i.e. patients diagnosed with LRR with or without associated distant metastasis at presentation). We will perform Cox proportional hazards regression for multivariate analysis and log-rank tests for univariate analysis, including potential prognostic factors as variables of interest.

9. Publication and authorship policy

All presentations and publications will be made on behalf of the MARECA study steering group. The steering group will be responsible for drafting manuscripts and preparing them for publication. Three levels of authorship are proposed based on degree of study participation:

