2.4 Study endpoints

2.4.1 Primary endpoint:

DFS following LRR resection in patients who present without distant metastasis, stratified according to the type of surgery performed for the primary breast cancer (BCS and radiotherapy vs. mastectomy).

2.4.2 Secondary endpoint:

-PFS in patients who present with LRR with distant metastasis.

-OS in patients with LRR +/- DM at presentation.

3. Definitions

For the purpose of this study, LRR is defined as diagnosis of invasive breast cancer or ductal carcinoma in situ in the ipsilateral breast (if applicable)/skin/chest wall/regional nodes (axilla/internal mammary/supraclavicular/infraclavicular) following previous breast cancer treatment with curative intent.

4. Methods

This is a prospective observational multicentre longitudinal cohort study. This will be a national research study in collaboration with the Association of Breast Surgery (ABS) Academic and Research committee, the Mammary Fold Academic and Research Collaborative (MFAC) committee, and the UK Breast Cancer Trainees Research Collaborative Group (BCTRCG).

The study will have 3 main phases;

- 1. National practice questionnaire on current management of patients diagnosed with LRR by breast MDTs across UK.
- Development of a national prospective cohort of patients newly diagnosed with LRR
 +/- DM in order to document management details for each patient with respect to their original and recurrent cancer.
- 3. Evaluating oncological outcomes of the study cohort at 3 and 5 years by collation and analysis of the data submitted from the participating centres.

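### The 165 per group (330 in total) is sized by logistic regression with equal groups, but DFS is to be analysed by log-rank and Cox regression with an expected 40/60 split

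*Protocol*

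**What the plan says.** The primary endpoint in Protocol section 2.4.1 is "DFS following LRR resection in patients who present without distant metastasis, stratified according to the type of surgery performed" for the primary cancer, that is, BCS with radiotherapy against mastectomy.

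Section 8 sizes this comparison. It expects a distribution of 40% mastectomy and 60% BCS. It states that "the 5 year DFS after treatment for LRR has been reported to be approximately 70" per cent, and takes the contrast from a single-centre retrospective study: "5 year DFS of 80% vs. 60" per cent. The calculation was done "using logistic regression analysis to adjust for other covariates stated in the background section (tumour and nodal staging, molecular receptor profile, and tumour grade"). It gives 165 patients in each group, and the section concludes: "Therefore, a subset of 330 patients diagnosed with LRR without distant metastasis will require recruiting to the study". The Gantt chart in the Appendix repeats 330 as the number required for the primary endpoint.

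The following paragraph of section 8 sets out the analysis. "Kaplan Meier survival analysis will be performed at the two study time points (3 and 5 years after diagnosis of LRR"), and "We will perform Cox proportional hazards regression for multivariate analysis and log-rank tests for univariate analysis, including potential prognostic factors as variables of interest". DFS is determined for patients without distant metastasis who go on to LRR resection. Logistic regression is not named as an analysis of DFS anywhere. No alpha, power, hazard ratio, number of events or covariate R² is given.

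**The concern.** A logistic model relates covariates to an event/no-event status and estimates an odds ratio. Log-rank and Cox methods use event times and censoring and estimate a hazard ratio, and their power depends on the number of events. The number offered as the requirement for the primary question was thus derived for a model that the plan does not apply to that question. It also assumes equal groups, where the same section expects 40/60.

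The figure is relied on: it is the protocol's only yardstick for whether the primary endpoint can be answered. A target in patients alone also gives no warning if events are scarcer than assumed. Because the protocol itself fixes both the sizing method and the analysis, this is not a detail left to a statistical analysis plan.

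**Working it through.** **Inputs from section 8.** 5-year DFS of 80% (BCS) and 60% (mastectomy); split 60/40; 165 per group; 330 in total.

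**Assumed, because not stated.** Two-sided alpha 0.05; power 80% or 90%; proportional hazards; complete 5-year follow-up; covariate R² (share of the variance of surgery type explained by the other covariates) from 0 to 0.5; all 330 patients analysable.

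**1. The plan's own figure.** For two proportions with equal groups, n per group = [1.96·√(2p̄q̄) + z_power·√(p₁q₁ + p₂q₂)]² / (p₁ − p₂)², with p̄ = 0.70.
- 80% power: (1.270 + 0.532)² / 0.04 gives 82 per group.
- 90% power: (1.270 + 0.811)² / 0.04 gives 109 per group.
- 95% power: 134 per group.
- 165 per group corresponds to about 98% unadjusted power.

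Dividing by (1 − R²) for covariate adjustment, 82 / 0.5 = 164 at 80% power, and 109 / 0.66 ≈ 165 at 90% power. A contrast of 60% versus 75% at 80% power with continuity correction also gives 165. Several unstated input sets fit, so 165 cannot be tied to one.

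**2. Allocation.** 330 × 0.4 = 132 mastectomy patients. To reach 165: 165 / 0.4 = 412.5, about 413 in total.

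**3. Events needed for the stated analysis at 40/60.** HR = ln 0.80 / ln 0.60 = 0.437, so ln HR = −0.828. Schoenfeld: events = (1.96 + z_power)² / [0.4 × 0.6 × (ln HR)²]. The mean 5-year event probability is 0.6 × 0.20 + 0.4 × 0.40 = 0.28.
- 80% power: 7.849 / 0.1646 = 47.7, so 48 events; 48 / 0.28 gives 172 patients.
- 90% power: 10.507 / 0.1646 = 63.8, so 64 events; 64 / 0.28 gives 229 patients.
- With R² = 0.5 these double to 96 events (343 patients) and 128 events (458 patients).

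**4. Power with 330 patients at 40/60.** Events = 132 × 0.40 + 198 × 0.20 = 92.4. Power = Φ(√[92.4 × 0.24 × (1 − R²)] × 0.828 − 1.96). The last column is the detectable hazard ratio at 80% power with events held at 92: exp(−2.80 / √[92 × 0.24 × (1 − R²)]).

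| R² | Cox power | Detectable HR, 80% power |
|---|---|---|
| 0 | 97% | 0.55 |
| 0.3 | 90% | 0.49 |
| 0.5 | 79% | 0.43 |

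**5. Does the change of model alone raise the requirement?** With equal groups at 80% power, the time-to-event calculation needs 46 events, 46 / 0.30 = 154 patients in total, against 2 × 82 = 164 for the binary comparison. With R² = 0.5 the figures are 307 and 328. It does not.

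**6. Why events should be stated.** Keep HR 0.437 but suppose 90% DFS after BCS; mastectomy DFS is then 0.90^(1/0.437) ≈ 79%. Events among 330 are about 198 × 0.10 + 132 × 0.21 ≈ 48, and power is about 80% at R² = 0 and 65% at R² = 0.3. This is an illustration, not a forecast.

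**The case against.** Sizing on a fixed-time proportion and analysing by Cox regression is a common approximation. Step 5 shows that it is mildly conservative here. The study is observational, has no statistical stopping rule and collects outcomes at fixed times, so an events target would not change its conduct. All of this stands, and it limits the weight of the point.

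Four stronger readings are tempting, but the document does not support them.
- *That 330 is too few.* At the protocol's own contrast, power stays at or above 90% for R² up to about 0.3 and falls just below 80% only near 0.5.
- *That 330 is uninformative about the Cox analysis.* It can be converted into events and power, as in step 4; the protocol simply does not do so.
- *That the protocol defines DFS as yes/no at 5 years.* It does not say so. This is inferred from the logistic model together with 5-year proportions.
- *That a logistic analysis of DFS will be run, dropping patients of unknown status.* No passage plans one; the logistic model appears only in the sizing.

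The objection does not remove the mismatch. Section 8 neither presents the logistic calculation as an approximation nor reconciles equal groups with its expected split.

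**Conclusion.** The point holds as a mismatch within section 8. The stated requirement of 165 per group matches neither the planned log-rank and Cox analysis nor the expected 40/60 allocation, under which 330 patients supply about 132 mastectomy patients. It is not a demonstration of inadequate power: the 97%, 90% and 79% in step 4 depend on the assumed alpha, R² range, follow-up and proportional hazards, and on the 80% versus 60% contrast being right.

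Those powers also take all 330 as analysable. Section 8 defines the 330 as patients without distant metastasis, whereas the endpoint counts only those who undergo LRR resection, so the analysable number may be smaller. The detectable hazard ratios hold events at 92. If mastectomy DFS is instead held at 60%, a weaker effect produces more events, and the unadjusted value is about 0.57 instead of 0.55. The point deserves correction because the figure is relied on and restating it is nearly free.

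**What to change.** In section 8, replace the logistic calculation with one for the adjusted Cox analysis at the expected 40/60 split. State alpha, power, target hazard ratio, the required number of DFS events, and the assumed covariate R² as a range. Count towards the target only patients without distant metastasis who undergo LRR resection, and allow for loss to follow-up. Drop the figure of 165 per group.

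If 330 is kept, describe it by the adjusted hazard ratio it can detect at 80% power: about 0.55, 0.49 and 0.43 for R² of 0, 0.3 and 0.5 with 92 events. Quoting 0.55 alone would give an unadjusted figure for an adjusted analysis. Align the Gantt chart entry with the revised wording.

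The cost is one recalculation and a reworded paragraph. The change itself requires no additional patients or data.
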